1.4 Sample Size

The sample size calculation for this 4-arm parallel-group study is based on the assumption of a SD of 2.0 and a paired t-test at the 0.05 alpha level. In this case, with 34 subjects per group, there is an 80% power to detect a 1-point difference in the CFB to Week 12 in DYS measured by NRS within a treatment group. This sample size is also expected to provide adequate precision in the point estimate and 95% CI of the CFB for each treatment group.

With an assumption that up to 10% of subjects may prematurely discontinue the study without providing data for efficacy evaluations, enrollment of approximately 38 subjects per treatment group is planned. Approximately 190 subjects will be screened to achieve 152 subjects randomly assigned to HMI-115 or placebo group and 136 evaluable subjects for an estimated total of 34 evaluable subjects per treatment group.

1.5 Randomization

All subjects will be centrally randomized using an Interactive Response Technology (IRT). The randomization will be stratified with two stratification factors 1) region and 2) participation in the intensive PK sampling subset. Each subject will be assigned a unique number (randomization number) that encodes the subject's assignment to different arms of the study.

Eligible subjects will be randomized into four arms: placebo, 60 mg, 120 mg, and 240 mg HMI-115 in a 1:1:1:1 ratio with 38 subjects/arm.

2. STATISTICAL CONSIDERATIONS

Data will be handled and processed per the sponsor's representative (Novotech) Standard Operating Procedures (SOPs), which are written based on the principles of good clinical practice (GCP).

2.1 General Considerations

- 'Baseline' is defined as the last available pre-treatment assessment (including unscheduled assessments) unless otherwise specified in the SAP.
- 'End of Study (EOS)' is defined as the last available post-treatment assessment.
- 'Study Day' will be calculated relative to the date of First Administration of IMP (i.e., prior to treatment, Study Day = Assessment Date -First Administration of IMP Date; otherwise, Study Day = Assessment Date - First Administration of IMP Date+1). The day of the first IMP administration will be Day 1. In case of partial or missing event date, study day will appear missing.
- Measurements collected at early discontinuation visit (EDV) will be mapped to the scheduled visit according to the analysis visit window in Table 12.2. If EDV measurement allocates to a visit without a scheduled measurement, EDV measurement will be considered for analysis by visit. If EDV measurement allocates to a visit with existing scheduled measurement, EDV measurement will not be considered for analysis by visit. Unscheduled visits will not be mapped to scheduled visits.
- For by-visit summaries, only scheduled assessments will be used in tables, and if there are repeated post-first dose assessments, only the earlier value will be used in summary. In the subject listing, data will be presented under the nominal visits.
- Continuous data will be summarized in terms of the number of observations (n), mean, standard deviation (SD), first quartile (Q1), median, third quartile (Q3), minimum and maximum, unless otherwise stated. The minimum and maximum will be reported to the same number of decimal places as the raw data recorded in the database. The mean, median, Q1 and Q3 will be reported to one more decimal place than the raw data recorded in the database. The SD will be reported to two more decimal places than the raw data recorded in the database. In general, the maximum number of decimal places reported shall be four for any summary statistic.
- Categorical data will be summarized in terms of frequency counts and percentages. Any planned collapsing of categories will be detailed in the SAP text and the data displays.
- Percentages will be presented to one decimal place. Percentages will not be presented for zero counts. Percentages will be calculated using n as the denominator unless otherwise specified. If sample sizes are small (n<10), the data displays will show the percentages, but any textual report will describe frequencies only.
- For quantitative measurements, change from baseline (CFB) at a particular visit will be calculated as (value at visit – baseline value).

Changes from baseline in categorical data will be summarized using shift tables where appropriate.

- P-values greater than or equal to 0.001, in general, will be presented to three decimal places after rounding. P-values less than 0.001 will be presented as "<0.001" and p-values greater than 0.999 will be presented as ">0.999".
- Confidence intervals (CIs) will be presented to one more decimal place than the point estimate.

- All values below or above a limit of quantification (e.g. <0.1 or >100) will be displayed as such in data listing. When include in table or figure summary, value may be substituted by specific value as described in corresponding section.
- For some safety parameters, the within-group and between-group differences are analyzed, but nominal p-values are provided for information only. No formal conclusion will be made based on p-values.
- For subjects who prematurely discontinued during the treatment period, their data collected during the Follow-up Period will be included in the analysis.

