- 17. Blood samples of sex hormones (PRL, LH, FSH, estradiol, progesterone, testosterone, DHEAS) could be taken on a separate day from the scheduled Visit Day to meet the menses cycle days 1 to 5.
- 18. eGFR will be calculated using the Chronic Kidney Disease Epidemiology Collaboration (CKD EPI) formula.
- 19. 12-ECG can be tested at any time apart from the specified timepoints if the subject feels uncomfortable. If QTc prolongation is found, including repeating PVCs confirmed by additional ECG examination at least 30 minutes apart, or QTcF >500 ms, or increase in QTcF interval >60 ms compared to baseline in the absence of possible causes other than the IMP, drug can be temporarily stopped to investigate the reason. See Section 7.1 for more details.
- 20. Vital signs include blood pressure, tympanic body temperature, pulse, and respiratory rate. Vital signs of subjects will be observed 1 hour after IMP administration on Day 1 and pre-dose at each visit.
- 21. Physical examination: for detailed information, refer to section 8.2.1.
- 22. Pelvic examination: for detailed information, refer to section 8.2.3 and 10.9.
- 23. e-Diary training will be provided at Visit 2, and e-Diary will be dispensed to record endometriosis associated pain (including NRS and scales for DYS, NMPP and DYSP), uterine bleeding, and rescue medication use for endometriosis associated pain on a daily basis from Visit 2 and at approximately the same time every day (morning preferred). Must be completed in the morning prior to arrival at the study site for study visits.
- 24. e-Diary entries compliance will be assessed and additional training will be provided to subjects who have missed data entry.
- 25. Rescue medication and education will be provided to subjects from Visit 2 for rescue use if needed for endometriosis associated pain throughout the study. Refer to table 6-3 for protocol allowed rescue medication.
- 26. All reported AEs to be checked for injection site reaction.
- 27. In addition to the listed sampling time, ADA will also be collected at week 17, together with PK sampling (not required for those who discontinued from IMP or withdraw from study).
- 28. Intensive and sparse PK blood sampling will be performed at timepoints specified in Table 1-2 and Table 1-3.

Note: Blood draws should be performed before vital signs, ECG recordings and physical examinations at visits (can be adjusted according to the condition of the site).

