7.1 Discontinuation of IMP

It may be necessary for a subject to permanently discontinue (definitive discontinuation) the IMP. If the IMP is definitively discontinued, the subject will remain in the study until Visit 10 to be evaluated for safety and efficacy of the IMP. Please refer to Section 10.4 and 8.4.5 for details on contraceptive guidance and collection of pregnancy information.

The Investigator or Medical Monitor (and, if needed, with DMC review) may temporarily hold or stop the dosing of IMP to a subject at any time during the study. For subjects that discontinue IMP for reasons related to safety, unblinding of the treatment assigned to the subject may be carried out if deemed necessary by the Sponsor to assess any potential safety signal or by the Investigator to provide adequate medical care to the subject. All details of reasons, therapies that may have been subsequently started should be well documented and reviewed.

Examples of conditions or symptoms that may warrant holding or stopping IMP at the Investigator's and/or Medical Monitor's discretion include:

- Occurrence of a severe or serious AE assessed as related to IMP
- Repeating premature ventricular contractions (PVC) confirmed by additional ECG examination at least 30 minutes apart, or QTcF interval >500 ms, or increase in QTcF interval >60 ms compared to baseline in absence of possible causes other than the IMP
- Significant decrease of neutrophils count < 1500 mm³ confirmed by repeat measurement

Version 6.0 45 of 138 April 11, 2024

- Pregnancy
- Intolerance of the IMP authorized under this protocol
- If in the Investigator's opinion, continuation with the administration of the IMP would be detrimental to the subject's well-being

Investigator must notify the Sponsor within one calendar day of being aware of an event that may warrant holding or stopping the IMP. If the IMP is held due to safety concerns, approval by the Medical Monitor is required prior to resumption of IMP. If the subject meets the holding or stopping conditions again after resumption (re-challenge), the IMP will be permanently discontinued.

Unless informed consent is withdrawn, subjects who permanently discontinue IMP during the treatment period should attend all subsequent visits up to Visit 10 and complete all procedures (except IMP administration related) as outlined in the SoA.

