8.4.2 Physical Examination

Physical examination abnormal findings will be summarized by treatment group and body system.

A by-subject listing of abnormal physical examination findings will be provided.

8.4.3 12-Lead ECG

ECG parameters, i.e., HR, PR, QT, QRS, QTcF, and QTcB will be summarized descriptively for each treatment group at each visit. The within-group CFBs will be summarized and will be compared with a paired t-test by visit; the between-group difference for each visit will be compared with an ANOVA, and two-sided 95% CI for the differences between each of the treatment groups and the placebo group will be presented.

The number and percentage of subjects with abnormal, clinically significant (CS) finding will also be summarized by treatment group at each visit.

ECG data will be listed by subject and visit including changes from baseline.

A summary of the number and percentage of subjects with QTcF intervals exceeding some predefined upper limits (e.g., >450ms, >480ms, >500ms for measured values as well as. >30ms, >60ms for CFBs) will be displayed in a frequency table.

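### The clinically significant ECG table omits symptom-driven and confirmatory ECGs, and the SAP does not say whether the QTcF threshold and laboratory shift tables include such values

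*SAP*

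**What the plan says.** **Rule for tables (SAP 2.1).** "For by-visit summaries, only scheduled assessments will be used in tables, and if there are repeated post-first dose assessments, only the earlier value will be" taken. The same section adds: "Unscheduled visits will not be mapped to scheduled visits". Early discontinuation measurements are mapped to an analysis visit if no scheduled measurement is already there. Baseline may come from an unscheduled assessment. Change from baseline for a quantitative measure is defined as the value at a given visit minus baseline.

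**ECG outputs (SAP 8.4.3).** "The number and percentage of subjects with abnormal, clinically significant (CS) finding will also be summarized by treatment group at each visit". The section then describes a frequency table of subjects whose QTcF exceeds limits on the measured value (such as 450, 480 and 500 ms) or on the change (such as 30 and 60 ms). No visit is mentioned for that table, and nothing is said about which ECGs feed it.

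**Laboratory outputs (SAP 8.3).** Descriptive statistics and changes are by visit. Shift tables are promised for every parameter, with no visit structure and no rule on repeats.

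**Where extra values come from (protocol).** Section 1.3, note 19: "12-ECG can be tested at any time apart from the specified timepoints if the subject feels uncomfortable". Section 7.1 gives examples that may warrant holding or stopping IMP. They include repeating ventricular contractions confirmed on a second ECG half an hour or more later, QTcF above 500 ms or up by more than 60 ms, and "Significant decrease of neutrophils count" to below 1500 on a repeat count. Table 2-1 names ventricular ectopic beats and neutropenia among the risks.

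**The concern.** The protocol generates unscheduled and repeat values for exactly the cardiac and neutrophil risks that it names. An ECG done because a subject feels unwell is more likely than a routine one to show an arrhythmia or a QTcF outlier. If the arm-level tables are built from scheduled values alone, they can under-count the findings that they exist to show. SAP 8.2 tabulates adverse events leading to IMP discontinuation. A temporary hold followed by resumption, which protocol 7.1 permits, has no table of its own; reasons for a dose not given appear only in listings (SAP 5).

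**Working it through.** The plan states no figure to reproduce. The check is a count from the schedule and a trace of each kind of value through the SAP outputs.

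**1. Scheduled post-first-dose assessments (protocol Table 1-1).** ECG: V4 to V10, so 7. Hematology: V5, V7 and V9 (Days 29, 57 and 85), so 3, with none at V10.

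**2. Timing against exposure.** At V4 to V8 tests precede that visit's dose, nominally 14 days after the previous one. V9 is 85 − 71 = 14 days after the last dose and V10 is 169 − 71 = 98 days after it. Protocol 2.2 puts peak concentration at about 4 to 11 days. No scheduled ECG is therefore nominally placed in the peak window. The contrast is limited, however. From protocol Tables 4-1 and 4-2 at 240 mg, predicted trough over peak is 9.76/12.4 = 0.79 after one dose and 27.3/36.6 = 0.75 at steady state.

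**3. Where an unscheduled or repeat value goes.**

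| Output | Described as by visit? | Unscheduled or repeat value |
|---|---|---|
| Clinically significant ECG table, SAP 8.4.3 | Yes | Omitted by stated rule |
| ECG and laboratory descriptive tables, SAP 8.4.3 and 8.3 | Yes | Omitted by stated rule |
| QTcF threshold table, SAP 8.4.3 | No | Not stated |
| Laboratory shift tables, SAP 8.3 | No | Not stated |
| Subject listings | Not a summary | Can appear; out-of-range laboratory values are flagged |
| Adverse event tables, SAP 8.1 and 8.2 | No | Enters if judged clinically significant and recorded as an adverse event |

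**4. The two silent outputs.** Because change from baseline is defined at a visit and unscheduled visits map to none, a programmer could exclude unscheduled values from the 30 and 60 ms change limits and from the shift tables. That argument does not reach the limits on the measured QTcF. Against it, the neighboring ECG table is expressly by visit and the QTcF table is not, so another programmer could include every ECG. Both readings are defensible and can give different counts.

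**5. Neutrophils, case by case.**
- Scheduled count low, repeat normal: the low value is kept.
- Scheduled count low, repeat confirms or is lower: the first low value is kept; the confirmation or the lower value is lost.
- Scheduled counts normal, fall seen only at an unscheduled draw: nothing appears in the by-visit table.

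The same logic applies to ECGs. A scheduled abnormal tracing stays and its confirmation drops out; a symptomatic tracing between visits leaves no trace in the by-visit table.

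**6. Scale.** One subject in a planned arm of 38 is 1/38 = 2.6%. This is only an illustration: SAP 3.3 and 8 set the safety set equal to the primary analysis set, whose arm sizes are not given.

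**The case against.** The strongest reply is that nothing is hidden. The rule governs by-visit summaries only. Protocol 8.2.5 requires clinically significant laboratory changes to be recorded as adverse events, and protocol 10.3.1 counts clinically significant ECG findings among adverse events. Palpitations are an event of special interest with their own tables. A related arrhythmia pauses the study for data monitoring committee review. Scheduled-only by-visit summaries are also sound practice, because they avoid over-weighting subjects who are retested. Keeping the earlier value stops a normal retest from overwriting an abnormal result. A baseline that admits unscheduled values is ordinary too. Finally, SAP 1 leaves detail to the table shells, which are not among the documents.

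Most of this stands. A reader might infer that symptomatic ECGs and confirmatory counts never count anywhere, or that an unscheduled QTcF above 500 ms would be reported as 0/38. The documents support neither inference: the values have other routes, and the QTcF table is silent rather than exclusionary. Nor does note 19 order an ECG or section 7.1 mandate a hold; both are permissive. The exposure argument is modest, given the trough-to-peak ratios above.

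What the reply does not answer is the by-visit table itself. Adverse event recording depends on the investigator's judgment, whereas a numeric threshold table does not. Listings give no rate by arm. If the shells already contain any-time rows, the SAP needs only to say so.

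**Conclusion.** The point holds in a limited form. One output, the clinically significant ECG table, omits symptom-driven and confirmatory ECGs by a stated rule. Two others, the QTcF threshold table and the laboratory shift tables, have no stated rule. The SAP text specifies no worst post-baseline ECG or laboratory summary and no count at the protocol's neutrophil level of 1500. For neutrophils the loss is narrower: a worse repeat, the confirmation, or a fall seen only between the 3 scheduled draws or after the last.

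The size cannot be stated in advance, because it depends on how many unscheduled tests are done. The conclusion assumes that the shells add nothing beyond the SAP text and that by-visit is read as SAP 2.1 writes it. This is a gap in safety reporting; it does not touch the efficacy analysis.

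It does not extend to prolactin. A reader might want the same any-time row for the prolactin category table, but protocol 1.3 (note 16) ties those samples to cycle days 1 to 5 and to avoiding opioids for two days beforehand. A worst value from any sample could mix cycle phase and opioid effects with the effect of treatment.

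**What to change.** Keep the by-visit rule in SAP 2.1.

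- **SAP 8.4.3:** add a row to the clinically significant ECG table for any time after first dose, counting unscheduled and repeat ECGs. State that the QTcF threshold table uses each subject's worst post-first-dose value from all ECGs.
- **SAP 8.3:** add a worst post-baseline shift for neutrophils using all post-first-dose values in the database, with a count of subjects below the protocol's 1500 level, split into confirmed and unconfirmed. Exclusion criterion 24 already bars subjects below that level at screening, so the count would mainly reflect later falls.
- **Prolactin:** leave the category table as it is.

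The cost is SAP and table-shell wording and a few extra rows. There are two limits. Protocol 10.2 allows safety repeats to be done locally, and the documents do not say how those results reach the database, so the new rows cover recorded values only; the SAP should say this. Worst-value counts also rise with the number of tests per subject, so an arm that is tested more often can look worse; giving the number of assessments per arm in a footnote would let readers judge that. No clinical hold or stopping rule changes.

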2.2 Inferential Analyses

The null hypothesis is that there is no difference between each HMI-115 treatment group and placebo in mean change of DYS measured by NRS from Baseline to Week 12 measurement. The alternative hypothesis will be that there is a difference.

All efficacy analyses will be conducted using the PAS. Each comparison will be carried out at the two-sided 5% level of statistical unless otherwise specified.

2.3 Multiple Comparisons and Multiplicity Adjustments.

Not applicable for this study.

2.4 Treatment Groups

Treatment groups will be summarized as follows:

- 60 mg
- 120 mg
- 240 mg
- Placebo
- Overall

Placebo treatment groups will be pooled for all analyses.

3. PARTICIPANT DISPOSITION AND ANALYSIS SETS

3.1 Participant Disposition

A clear accounting of the disposition of all subjects who enter the study will be provided, from screening to study completion.

The number and percentage of subjects entering and completing the clinical study will be presented for all subjects enrolled by treatment group and overall. Subject disposition will be summarized and will include the following information: number and percentage of subjects enrolled, screen failed, reason for screen failures, number and percentage of subjects randomized and dosed, number and percentage of subjects completing the study and the number and percentage of subjects who were withdrawn (including reasons for withdrawal and including discontinuing IMP/discontinuing study).

By-subject listings of informed consent details, eligibility details, randomization details, visit dates and withdrawal/study completion details (including reason for discontinuation and duration of treatment prior to discontinuation) should be provided.

3.2 Protocol Deviations

Major protocol deviations and any action to be taken regarding the exclusion of patients or affected data from specific analyses are defined in the project-specific Protocol Deviation Specification.

All protocol deviations will be reviewed and classified on a Blinded Data Review Meeting (BDRM) shortly before database lock/unblinding. Results and analysis set assignments will be summarized in a BDRM report which will be signed off by all relevant scientific experts.

The number and percentage of subjects with any major protocol deviations and any major protocol deviations related to COVID-19 will be presented for treatment group by deviation category using all subjects randomized.

A by-subject listing of protocol deviations will also be presented. Protocol deviations related to COVID-19 will be identified.

3.3 Analysis Sets

For purposes of analysis, the following analysis sets will be used:

Analysis Set	Description
Enrolled Analysis Set (ES)	All subjects who signed the ICF (including screening failures).
Full Analysis Set (FAS)	All randomized subjects who take at least one dose of IMP. For the FAS, subjects are assigned to a treatment group based on the randomization schedule, regardless of the treatment actually received.
Primary Analysis Set (PAS)	All subjects in the FAS who have surgical diagnosis. PAS will be the primary analysis set for all efficacy analyses.
Per Protocol Analysis Set (PPS)	A subset of the PAS who do not have protocol deviations that could significantly affect the results for the primary endpoints. Subjects' inclusion/exclusion from the PPS will be determined and documented prior to the database lock and unblinding. PPS will be used to demonstrate robustness of results for the primary and secondary efficacy endpoints.
Safety Analysis Set (SAF)	All subjects who received at least one dose of IMP. Subjects will be analyzed according to the IMP they actually received. SAF

	will be used for all safety analyses. In the SAP V1.3 special version for research paper publication, the SAF will be same as the PAS.
PK Analysis Set (PKS)	All subjects in the SAF who received active treatment with at least one drug concentration value, and have no major protocol deviation that could significantly impact PK assessment.
Immunogenicity Analysis Set	The immunogenicity analysis set consists of all subjects in the SAF with at least one immunogenicity value.

All protocol deviations will be reviewed and classified regarding how they affect clinical and analysis outcomes during the BDRM. Subjects may be excluded from the PPS and PKS.

Summary of the number and percentage of subjects in each analysis set with exception of the ES by treatment group and overall, based on all randomized subjects with reasons for exclusion from each analysis set will be provided.

A by-subject listing of analysis set details will be provided on the ES. This listing will be presented by treatment group and will include center, subject identifier, inclusion/exclusion flag for each set and reason for exclusion from each set.

